1 ABBREVIATIONS

AE	Adverse event
ALT	Alanine aminotransferase
APTT	Activated partial thromboplastin time
AST	Aspartate aminotransferase
CRF	Case report form
CSF	Cerebrospinal fluid
DNA	Deoxyribonucleic Acid
DSMB	Data safety monitoring board
CRF	electronic case report form
EKG / ECG	Electrocardiogram
FAS	Full analysis data set
FDA	Food and Drug Administration
GCP	Good clinical practice
GGT	Gamma glutamyl transferase
IMP	Investigational Medicinal Product
INR	International normalized ratio
IRB / IEC	Institutional Review Board / Independent Ethics Committee
MS	Multiple sclerosis
NCV	Nervous conduction velocity
NIMP	Non investigational medicinal product
PC	Personal computer
PP	Per protocol
PT	Prothrombin time
QoL	Quality of life
RBC	Red blood cell
SAE	Serious adverse event
SAP	Statistical analyses plan
SD	Standard deviation
SUSAR	Suspected unexpected serious adverse reaction
WBC	White blood cell

2 STUDY SUMMARY

Study Protocol Title	SERENDEM study: MD1003 in patients suffering from demyelinating neuropathies, an open label pilot study
Short title	SERENDEM
Study Protocol Number	MD1003CT2015-01-SERENDEM
EudraCT Number	2015-001150-15
Methodology and study design	open label, uncontrolled, pilot study in 3 distinct groups of 5 patients suffering from a specific aetiology pattern of peripheral neuropathy
Study Center	Henri Mondor Hospital, Créteil France
Objectives	To assess efficacy of MD1003 given orally thrice a day on motor and sensory conduction, in patients suffering from demyelinating polyneuropathies.
Number of patients	15 patients: 3 groups of 5 patients (CIDP, anti-MAG, CMT1a, CMT1b)
Diagnosis and main inclusion criteria	
 • Male and female aged between 20 and 85 years. • Patients fulfilling one of the following diagnosis on both clinical and neurophysiological grounds, either with: 
 • CIDP • proven genetic diagnosis of CMT1a • proven genetic diagnosis of CMT1b • anti-MAG polyneuropathy • Electrophysiological parameters worsening for the past 3 years • Available EMG record, performed during the past 6 months to assess variability of NCV parameters • Having given informed consent
Non-inclusion criteria	
 • For CIDP patients, relapse in the past 3 months before inclusion • Pregnancy • Women of childbearing potential without effective contraception
Investigational Product	MD1003, 100 mg capsule
Control therapy	No control arm
Concomitant therapies	Best standard of care
Duration of administration	48 weeks
Evaluation criteria	Primary objective:

	
The primary endpoint will be evaluated as follows: significant change from baseline to week 48 in at least two out of the four criteria of demyelination:
 
 • motor nerve conduction velocity, • distal latency, • F wave latency, • length of motor nerve potential, 
8 nerves will be assessed for those 4 parameters. Change will be considered significant when the last value is 10% improved compared to the baseline value for 2 out of the 4 parameters in at least 3 nerves out of 8 investigated nerves.
 
The secondary endpoints are changes from baseline to week 48 in ONLS, MRC, INCAT, Posturometry, Timed 10-meter walk test, 6-min walk test, Min-max absolute refractory period, Refractoriness, Supernormality, Strength-duration time constant, Rheobase
 
Secondary objective: To evaluate the safety of high doses of biotin.

Statistical methodology	Exploratory descriptive analyses
Duration of patient participation	48 weeks
Study duration	52 weeks

3 STUDY RATIONALE – HISTORICAL BACKGROUND

3.1 Disease aetiology, pathology, symptomatology and current treatments

3.1.1 Aetiology

3.1.1.1 Chronic inflammatory demyelinating polyradiculoneuropathy

Chronic inflammatory demyelinating polyradiculoneuropathy (CIDP) is an acquired paralytic illness affecting peripheral nerves and caused by a demyelinating process.

CIDP is a rare disease. The various epidemiological studies show that prevalence may vary from 1.24/100 000 (Laughlin 2009) to 8.9/100 000 (Mahdi-Rogers 2013). Due to the ambiguities of diagnosing CIDP, the true prevalence of the disease may be underestimated or overestimated. The etiology of CIDP is unknown even if rare cases can be associated with different conditions, such as diabetes mellitus, sarcoidosis, disseminated lupus erythematosus, or idiopathic monoclonal gammopathy.

3.1.1.2 Demyelinating neuropathy associated with immunoglobulin M (IgM) monoclonal gammopathy and antibodies against myelin-associated glycoprotein (MAG)

Polyneuropathy associated with IgM monoclonal gammopathy and antibodies against myelin-associated glycoprotein (MAG) belongs to the group of chronic demyelinating polyneuropathies. It is a chronic progressive disorder that leads to a variable degree of functional impairment and disability.

3.1.1.3 Charcot Marie Tooth Ia and Ib (CMT Ia and Ib) neuropathy

Charcot-Marie-Tooth disease Type 1A (CMT1a) belongs to the group of inherited, progressive, chronic sensory and motor peripheral neuropathies referred to as Charcot-Marie-Tooth (CMT) disease or as “Hereditary Motor and Sensory Neuropathy” (HMSN). CMT1a accounts for 70% of patients with CMT, with an estimated prevalence of 10 in 100,000. CMT1a is an autosomal dominant disorder caused in the vast majority of cases by a 1.4 megabase-long duplication of chromosome 17p11.2, encompassing the PMP22 gene.

Charcot-Marie-Tooth disease Type 1B (CMT1b) belongs to the group of inherited, progressive, chronic sensory and motor peripheral neuropathies referred to as Charcot-Marie-Tooth (CMT) disease or as “Hereditary Motor and Sensory Neuropathy” (HMSN). CMT1b accounts for 6%-10% of patients with CMT, with an estimated prevalence of 1.5:100.000. CMT1b is an autosomal dominant disorder caused in the vast majority of cases by mutations change in the single protein building blocks (amino acids) in myelin protein zero (MPZ), located in the chromosome 1.

3.1.2 Clinical symptoms and evolution

3.1.2.1 Chronic inflammatory demyelinating polyneuropathy

Chronic inflammatory demyelinating polyneuropathy (CIDP) is an immune neuropathy; its diagnosis has challenged physicians since its first description by Dyck and others (Dyck, 1975). As a result, this condition has undergone more than 10 revisions of its diagnostic criteria (Dyck, 1975; Hughes *et al.*, 2001; 2005; Barohn *et al.*, 1989; Nevo and Topaloglu, 2002; Saperstein *et al.*, 2001; Thaisethawatkul *et al.*, 2002; Magda *et al.*, 2003; AAN task Force, 1991; Joint Task Force of the EFNS and the PNS, 2010). These criteria are based mainly on clinical and neurophysiological parameters that may help distinguish CIDP from other neuropathies, including chronic idiopathic axonal polyneuropathy, diabetic polyneuropathies and amyotrophic lateral sclerosis. Furthermore, several variants of inflammatory neuropathy have been defined, including multifocal motor neuropathy with conduction blocks, multifocal motor and sensory neuropathy with conduction blocks and distal acquired demyelinating polyneuropathy (Larue *et al.*, 2011; Viala *et al.*, 2010).

The most recent recommendation by the European Federation of Neurological Societies allows for the distinction among definite, probable and possible CIDP diagnoses based on the clinical diagnostic criteria of typical CIDP and atypical CIDP (Joint Task Force of the European Federation of the Neurological Societies [EFNS] and the Peripheral Nerve Society [PNS], 2010). The clinical diagnosis of typical CIDP is easier to identify than the diagnosis of atypical CIDP due to the possibility of variants with pure motor or pure sensory presentations and asymmetric or focal presentations with atypical CIDP. Moreover, the existence of several neurophysiological classifications of demyelination and the possibility of presentations with axonal features exacerbates the process of accurate classification.

Typical CIDP is characterized by a chronically progressive, stepwise, or recurrent symmetric proximal and distal weakness and sensory dysfunction of all extremities, developing over at least 2 months; cranial nerves may be affected; and absent or reduced tendon reflexes in all extremities.

Atypical CIDP (still considered CIDP but with different features) may have normal tendon reflexes in unaffected limbs: predominantly distal (distal acquired demyelinating symmetric, DADS) or asymmetric [multifocal acquired demyelinating sensory and motor neuropathy (MADSAM), Lewis-Sumner syndrome] or focal (e.g., involvement of the brachial or lumbosacral plexus or of one or more peripheral nerves in one upper or lower limb); or pure motor; or pure sensory (including chronic immune sensory polyradiculopathy affecting the central process of the primary sensory neuron) neurological deficits.

The temporal course may be characterized by a subacute onset or acute onset, a relapsing-remitting course or a progressive course (Joint Task Force of the EFNS and the PNS, 2010). The long term prognosis of CIDP patients is not so good after five years with 39% of patients still requiring immune treatments and 13% with severe disabilities (Kuwabara 2006). The prognosis of CIDP is related to axonal loss secondary to inflammatory demyelination (Hughes et al., 2006; van Schaik et al., 2006).

3.1.2.2 *Demyelinating neuropathy associated with immunoglobulin M (IgM) monoclonal gammopathy and antibodies against myelin-associated glycoprotein (MAG)*

Polyneuropathy associated with IgM monoclonal gammopathy and antibodies against myelin-associated glycoprotein (MAG) is a chronic progressive disorder that leads to a variable degree of functional impairment and disability. Most patients have a symmetric sensorimotor polyneuropathy, sensory ataxia, painful paresthesia and upper limb tremor. The disease may progress slowly over many years in some patients, whereas others develop significant disability mostly due to dysesthesia and ataxia; thus, there is a need to develop effective treatments (EFNS and PNS guideline, 2010).

3.1.2.3 *Charcot Marie Tooth Ia and Ib (CMT Ia and Ib) neuropathy*

Typical clinical features of CMT1A and CMT1B are similar including weakness of the foot and lower leg and foot deformities (most frequently pes cavus), which appear to be due to weakness of the small intrinsic muscles of the feet. Later in the disease, weakness and muscle atrophy may occur in the hands, resulting in difficulty with fine motor skills. The severity of symptoms is quite variable from one patient to another and even among affected members of the same family.

3.1.3 *Pathophysiology*

3.1.3.1 *Chronic inflammatory demyelinating polyneuropathy*

The underlying pathologic mechanisms are still unclear but an autoimmune aetiology is probable. Various mechanisms may be instrumental in CIDP including presence of auto-antibodies, inflammatory mediators (tumor necrosis factor alpha, interleukin 1, matrix metalloproteinases 2 and 9, complement fractions, chemokines), lymphocyte proliferation, modulation of the Fcγ RII / Fcγ RIII ratio on macrophages. Whatever the involved mechanisms, the consequences include alteration of nerve excitability due to demyelination, decrease of Na⁺/K⁺ ATPase pump function, intra-axonal Na⁺ accumulation associated with energetic failure, leading process to axonal degeneration in inflammatory demyelinating processes (Stys and Waxman, 1994; Bechtold and Smith, 2005).

3.1.3.2 *Demyelinating neuropathy associated with immunoglobulin M (IgM) monoclonal gammopathy and antibodies against myelin-associated glycoprotein (MAG)*

A causative role of the IgM M protein in the polyneuropathy is illustrated by the presence of circulating anti MAG antibodies or other antibodies directed at the myelin sheath of peripheral nerves that lead to enlargement of the myelin sheath. Patients present with a striking immunochemical profile, suggesting the possibility of an autoimmune mechanism: monoclonal IgM recognizes a carbohydrate MAG epitope, which is shared with a number of other glycoconjugates involved in cell adhesion, including the Po glycoprotein of myelin, peripheral myelin protein-22, sulfated sphingolipid, and other related glycolipids (Latov et al. , 1995; Eurelings et al., 2001). The nerve examination shows widening of myelin lamellae.

3.1.3.3 *Charcot Marie Tooth Ia and Ib (CMT Ia and Ib) neuropathy*

PMP22 encodes a transmembrane peripheral myelin protein. The duplication of the PMP22 gene results in its overexpression and in abnormal Schwann cell differentiation. The consequences are a homogeneous and diffuse nerve conduction slowing and dysmyelination, eventually leading to axonal loss and muscle wasting.

The altered myelin protein zero probably cannot interact properly with other myelin components, which may disrupt the formation and maintenance of myelin. As a result, peripheral nerve cells cannot activate muscles used for movement or relay information from sensory cells back to the brain, leading to the weakness and sensory problems characteristic of Charcot-Marie-Tooth disease.

3.1.4 *Current treatments*

3.1.4.1 *Chronic inflammatory demyelinating polyneuropathy*

Corticosteroids, plasma exchange, and intravenous (IV) immunoglobulin (IVIg) have shown efficacy in controlled trials. The choice of therapy depends on several factors, including disease severity, concomitant illnesses, adverse-effect profile, potential drug interactions, venous access, age-related risks, and cost of treatment. Corticosteroids is considered as a first line or second line treatment option and have been used to treat CIDP for a long time. It is usually initiated with a dose of 1mg/kg with a tapering after several months according to clinical response. IVIg is widely used in the treatment of CIDP. Treatment by intravenous immunoglobulins, (IVIgs) can provide significant clinical benefits in more than 60% of CIDP patients (Vermeulen et al., 1993; Hahn et al., 1996; Mendell et al., 2001). Clinical improvement often occurs within a few days following IVIg infusions (Kaji et al., 1992; Chaudhry et al., 1993; Nobile-Orazio et al., 1993; Van den Berg et al., 1995; 1998; Léger et al., 2001). However, such improvement usually lasts for a few weeks and periodic IVIg infusions are required to maintain therapeutic benefit. Finally, the long term effect of IVIG has not been investigated for more than 6 months (Hughes 2009). Moreover, there is no data on the prevention of axonal degeneration with these treatment options.

3.1.4.2 *Demyelinating neuropathy associated with immunoglobulin M (IgM) monoclonal gammopathy and antibodies against myelin-associated glycoprotein (MAG)*

There is no consensus about the best treatment strategy, besides the timing of initiation of treatment has not been determined for anti-MAG neuropathy. Immunotherapy and chemotherapy may act through direct suppression or elimination of the B cell clone, or by suppression of the inflammatory cascade (Lunn et Al. 2012). There is insufficient evidence from most pilot studies or randomized controlled trials (RCT) on IgM anti-MAG demyelinating neuropathy to recommend any particular immunotherapy. The last controlled trial for rituximab did not show any benefit (Léger et Al. 2013).

3.1.4.3 *Charcot Marie Tooth Ia and Ib (CMT Ia and Ib) neuropathy*

There is currently no approved treatment for CMT1A and for CMT1B. Supportive therapies mainly address disease symptoms such as neuropathic pain, weakness and limb deformities. They include

treatment of pain (anti-inflammatory/analgesics, anti-depressants or anti-convulsants for neuropathic pain), physiotherapy (muscle strength training), occupational therapy, orthopaedic devices (including braces and high top shoes) and orthopaedic surgery. However, these treatments are not sufficient to limit impairment of motor function and worsening of disability. Ascorbic acid (AA) has shown to promote myelination in vitro and to possibly decrease PMP22 expression. Following this, six clinical trials assessing efficacy and tolerability of 1- or 2-year AA treatment were published, but no clinical benefit was observed in any of these trials. In addition, the results from a double-blind, randomized, placebo-controlled dose ranging phase 2 study of PXT3003 (a low dose combination of three already approved compounds: (RS)-baclofen, naltrexone hydrochloride and D-sorbitol) were recently published. This trial confirmed the potential good safety and tolerability of PXT3003. The highest dose showed preliminary but consistent evidence of efficacy, with a modest clinical benefit in these adult patients.

3.2 Summary of findings from nonclinical and clinical studies with biotin

3.2.1 Roles of biotin in normal cell metabolism

Biotin (or vitamin H) is a ubiquitous water-soluble vitamin which is naturally found in many foods, such as offal, eggs and some vegetables. In mammals, biotin acts as a coenzyme for four important carboxylases involved in key steps of energy metabolism and fatty acids synthesis. Biotin-dependent mitochondrial carboxylases include PC (pyruvate carboxylase), PCC (propionyl CoA carboxylase), and MCC (methylcrotonyl CoA carboxylase). All these three enzymes ultimately provide intermediates for the Krebs cycle including acetyl CoA, succinyl-CoA and oxaloacetate. These anaplerotic reactions trigger increased ATP production in neurons (Rinholm et al., 2011).

3.2.2 Biotin and biotin-responsive basal ganglia disease “BBGD”.

High doses of biotin have been demonstrated to be a therapeutic option in “biotin responsive basal ganglia disease”, an orphan neurometabolic disease (Ozand et al., 1998; Debs et al., 2010) which is caused by mutations in the SLC19A3 gene coding for a thiamine transporter (Zeng et al., 2005; Subramanian et al., 2006). A hypothesis explaining the effect of high doses of biotin in BBGD is that biotin activates the Krebs cycle downstream of the pyruvate and α -ketoglutarate dehydrogenases that are impaired in situations of defect in thiamine transport.

3.2.3 Biotin and primary or secondary progressive multiple sclerosis

Previous human experience in a pilot study and results of two phase IIb/III studies (EudraCT No. 2013-002113-35 and 2013-002112-27, namely MS-SPI study and MS-ON study, respectively) have provided evidences of a favourable benefit/risk balance of MD1003 (biotin 300 mg/day) in adult patients with progressive MS, but not in MS patients with relapsing-remitting MS.

The randomized, double-blinded MS-SPI study included adult patients with PP and SP MS with no evidence of inflammatory activity (n=103 in the MD1003 group and n=54 in the placebo group). Improvement was defined as either a decrease in disability score (EDSS) or an improvement in TW25 (a timed 25-foot walk) as compared to the best EDSS and TW25 scores obtained either at the screening or randomisation visits. Results demonstrated a strong and clinically meaningful benefit of MD1003 compared to placebo with (1) improvement of a significant proportion of patients after 9 months confirmed at 12 months (primary endpoint, p=0.005), (2) stabilized mean EDSS score (p=0.014) and (3) better clinical global impression of change (p<0.0001).

The randomized, double-blinded MS-ON study included adult patients with either visual loss following an optic neuritis relapse (ON relapses, n=62) or chronic progressive optic neuritis (progressive ON, n=31). The primary endpoint was the mean change in 100% contrast visual acuity (VA) at 6 months from baseline of the worst eye. In patients with ON relapses, VA improved in both placebo and MD1003 groups by a mean of 0.06 LogMAR, i.e. 3 letters in both groups, without any superiority of MD1003. In the progressive ON subgroup, VA worsened by a mean of 0.03 LogMAR in the placebo group, while it improved by a mean of 0.06 LogMAR in the MD1003 group. Although the number of patients was too

small to reach statistical significance, these results are in line with the positive results of the MS-SPI trial and indicate that MD1003 should be indicated in progressive MS only.

It is hypothesized that the positive effects of high doses of biotin in progressive MS are linked to:

(1) Increased energy production in demyelinated neurons. This would avoid neurodegeneration and would improve neuronal functioning.

(2) Stimulation of myelin repair through activation of the acetyl CoA carboxylase in oligodendrocytes. This induction of myelin repair could explain the very long-term effects of the treatment with continuous improvement overtime even after 14 months of treatment.

We hypothesized that chronic inflammatory demyelinating polyradiculoneuropathy, demyelinating neuropathy associated with immunoglobulin M (IgM) monoclonal gammopathy and antibodies against myelin-associated glycoprotein (MAG), Charcot Marie Tooth Ia and Ib (CMT Ia and Ib) neuropathy and progressive multiple sclerosis share some similarities including demyelinating processes, and chronic progressive disorders leading to a variable degree of functional impairment and disability.

Considering previous positive results in progressive MS it is justified to investigate the MD1003 in a population of demyelinating neuropathies of different aetiologies, as a proof of concept / pilot study using various measurement methods.

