5.3 Selection and withdrawal of patients

5.3.1 Inclusion criteria

Patients must fulfill all the following criteria:

- Male and female aged between 20 and 85 years.
- Patients fulfilling one of the following diagnosis:
 - Five patients with chronic inflammatory demyelinating polyneuropathy on both clinical and neurophysiological grounds.
 - Five patients with proven genetic diagnosis of CMT1a or CMT1b
 - Five patients with anti-MAG polyneuropathy.
- Electrophysiological parameters worsening for the past 3 years
- Available EMG record, performed during the past 6 months to assess variability of NCV parameters
- Signed and dated written informed consent to participate in the study in accordance with local regulations
- Likely to be able to participate in all scheduled evaluation and complete all required study procedures,
- In the opinion of the investigator, the patient will be compliant and have a high probability of completing the study.
- Both male and female subjects who are not either surgically sterile (tubal ligation/obstruction or removal of ovaries or uterus) or post-menopausal (no spontaneous menstrual periods for at least one year confirmed by a negative hormone panel) must commit to using **TWO** highly effective method of birth control for the duration of the study and for two months after the treatment termination. A highly effective method of birth control is defined as those which result in a low failure rate (i.e., less than 1% per year) when used consistently and correctly such as implants, injectable or combined oral contraceptives, IUDs, sexual abstinence or vasectomized partner. Acceptable forms of effective contraception include:

- Established use oral, injected or implanted hormonal methods of contraception.
- Placement of an intrauterine device (IUD) or intrauterine system (IUS).
- Barrier methods of contraception: Condom or Occlusive cap (diaphragm or cervical/vault caps) with spermicidal foam/gel/film/cream/suppository. Notice that, when used alone, the diaphragm and condom are not highly effective forms of contraception.
- The use of additional spermicides does confer additional theoretical contraceptive protection. Spermicides alone are inefficient at preventing pregnancy when the whole ejaculate is spilled. **Therefore, spermicides are not a barrier method of contraception and should not be used alone.**

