Overall the four limbs will be investigated, including one motor and one sensitive nerve for a total of maximum 8 nerves. The same protocol will be applied at each visit for one patient, aiming to record on the same nerves the studied demyelination criteria.

The investigator will be free to define the most relevant protocol according to patient disease status at baseline. However, the same protocol will be applied in a patient all along the study and the investigator will apply his best efforts to comply with this rule.

5.7.1.1.1 **Polyneuropathy protocol:**

1. Test most involved limb first if mild; if severe do least involved limb first.
2. Test at least 2 limbs, upper and lower, do 3rd limb for symmetry.
3. Lower extremity do sural sensory, peroneal motor with conduction, tibial motor with an F-wave.
4. Upper extremity do a sensory either median or ulnar, also a motor either median or ulnar with conduction and an F-wave.

5.7.1.1.2 **Polyradiculopathy protocol**

1. Sural sensory ankle; stimulate 14 cm proximal to recording electrode.
2. If sural equivocal or technically difficult:
 - a. Opposite sural
 - b. Median sensory (index); stimulate at wrist and elbow.
3. Peroneal motor (EDB); stimulate at knee and ankle with F-response latency.
4. Tibial motor (abductor hallucis brevis); stimulate knee and ankle with F-response latency.
5. Ulnar motor (hypotenar); stimulate at wrist and elbow with F-response latency.
6. If clinically indicated, consider:
 - a. Median (thenar); stimulate at wrist and elbows with F-response latency.
 - b. Musculocutaneous (biceps brachii); stimulate at axilla.
 - c. Facial (orbicularis oculi); stimulate at ankle of jaw.

d. Trigeminal (orbicularis oculi); stimulate supraorbital nerve.

Electrophysiological measures will be performed at W0, W24 and W48 and following parameters will be recorded in the CRF:

- motor nerve conduction velocity,
- distal latency,
- F wave latency,
- length of motor nerve potential

5.7.1.2 *Excitability testing*

Nerve excitability testing is a non-invasive approach in investigating the pathophysiology of peripheral nerve disorders, which determines the electrical properties of the nerve membrane at the site of stimulation

5.7.1.3 *Medical Research Council (MRC) sum score*

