2 SUMMARY OF CHANGES TO THE PROTOCOL

2.1 Changes to the conduct of the study

Classical MRC sum score with 6 muscles was planned in the protocol for the assessment of muscle strength. In the context of peripheral neuropathies an extended version of this MRC involving 19 muscles was used.

Safety data were to be reviewed on a regular basis by the Data Safety Monitoring Boards (DSMB) (see protocol section 11.8.2). It was the Sponsor decision not to implement a DSMB in this open labelled non-controlled study based on FDA's guidance for clinical Sponsor "Establishment and Operation of Clinical Trial Data Monitoring Committees".

Weight measurement is not in the investigator day to day practice and was omitted.

Posturography was not performed in the same conditions as described in the protocol as the equipment available on site (dynamometric platforms Bertec 400*600mm (Bertec Corporation, Columbus, OH, USA) with a recording frequency of 1000 Hz) is different.

Data related to the center of pressure of the Posturography parameters were collected instead of data related to center of gravity.

Additionally, in agreement with the sponsor, the trial site has merged the selection visit with the inclusion visit for all the patients, leading to a single one-day visit.

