3.4 Baseline data

Baseline data will be defined as the last non missing value available before the first administration of study treatment.

For all data collected both at selection visit (Visit 1) and inclusion visit (Visit 2), the baseline value will be defined as the assessment closest to and before the start of study medication, *i.e.* visit 2. The selection visit (visit 1) will be taken if the value is not available at inclusion visit.

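### Success at week 48 is scored against one W0 reading, with no control and no confirmation, so measurement error can create chance responders; the earlier EMG that could show how many is not analysed

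*Protocol*

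**What the plan says.** **Success rule.** Under SAP 10.1.1 a patient succeeds if the week 48 value is at least 10% better than baseline on two of four criteria in three of up to eight nerves. Week 24 plays no part, except that LOCF lets it replace a missing week 48 value (SAP 3.2).

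**Baseline.** For measures taken at both early visits, SAP 3.4 says "the baseline value will be defined as the assessment closest to and before the start of study medication". Protocol 5.6.2 lists a neurophysiological examination at W-4 as well as W0. The schedule in 5.6.1 does not, and Protocol 5.7.1.1 says "Electrophysiological measures will be performed at W0, W24 and W48". In the event, "the trial site has merged the selection visit with the inclusion visit for all the patients, leading to a single one-day visit" (SAP 2.1). Each patient therefore has one on-study pre-treatment examination.

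**Eligibility.** Protocol 5.3.1 requires "Electrophysiological parameters worsening for the past 3 years" and also "Available EMG record, performed during the past 6 months to assess variability of NCV parameters". It does not say which readings establish the worsening or how large it must be. The SAP contains no analysis of the earlier EMG.

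**Control.** There is none. Protocol 4 says the study should assess intra-individual variability and the robustness of the criteria, and should inform the sample size of a placebo-controlled trial.

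**Earlier MD1003 trial.** Protocol 3.2.3 describes MS-SPI as randomised and double-blind, with improvement scored "as compared to the best EDSS and TW25 scores obtained either at the screening or randomisation visits" and a primary result of "improvement of a significant proportion of patients after 9 months confirmed at 12 months".

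**The concern.** A single reading carries measurement error. When the baseline reading happens to be poor, a later reading looks improved even though the nerve has not changed. The success rule has 32 nerve-criterion comparisons (8 × 4) and needs only a small subset of them to cross 10%. Error shared within a session makes crossings cluster in the same patient.

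In a controlled trial such chance successes would appear in both arms. Here nothing separates them from a drug effect, and the SAP states no null response rate against which to read the percentage. The study is described as able to pick up an efficacy signal in 15 patients (SAP 1.3) and is meant to feed the planning of a larger trial. Two or three chance responders would matter for both purposes.

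**Working it through.** **Plan's own figure.** The 15 patients are 3 × 5. The documents give no effect size, error SD, null rate or power, so there is nothing further to reproduce.

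**Inputs from the documents.** 10% threshold; two of four criteria; three of at most eight nerves; improvement is an increase in velocity and a decrease in the other three criteria (SAP 10.1.1).

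**Assumptions.** No true change. Log-normal error with SD *s* per reading, 3% to 10%. A share of 0.3 or 0.5 of the error variance is common to all readings in a session and acts in the same clinical direction. Eight nerves, all four criteria evaluable. The rule is read as two criteria that each improve in at least three nerves.

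**Step 1: one nerve-criterion.** The log change between two readings has SD *s*√2. The chance of an apparent 10% improvement is 1 − Φ(ln 1.10 / (*s*√2)) for velocity and 1 − Φ(−ln 0.90 / (*s*√2)) for the other criteria.

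| *s* | velocity | other three |
|---|---|---|
| 3% | 1.2% | 0.6% |
| 5% | 8.9% | 6.8% |
| 7% | 16.8% | 14.4% |
| 10% | 25.0% | 22.8% |

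Example at 7%: 0.0953 / 0.0990 = 0.963, giving 16.8%.

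**Step 2: the patient-level rule,** by simulation (100,000 patients per setting). Each pair is for shared variance 0.3 / 0.5.

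| *s* | single W0 | expected in 15 | better of earlier EMG and W0 | expected in 15 |
|---|---|---|---|---|
| 3% | 0.1 / 0.3% | under 0.1 | 0.0 / 0.0% | 0 |
| 5% | 5.5 / 7.9% | 0.8–1.2 | 0.4 / 1.3% | 0.1–0.2 |
| 7% | 18.4 / 20.3% | 2.8–3.0 | 3.3 / 5.7% | 0.5–0.9 |
| 10% | 35.2 / 34.1% | 5.1–5.3 | 10.6 / 13.5% | 1.6–2.0 |

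Example: 15 × 0.184 = 2.8. The chance of at least one chance responder at 7% is 1 − (1 − 0.184)^15, about 95%.

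**Step 3: what moves the single-baseline rate.**
- Other reading of the rule (three nerves, each with two improved criteria): 17.4 / 19.5% at 7%.
- Only four evaluable nerves at 7%: 3.4 / 6.9%, or 6.5 / 10.3% under the other reading.
- A true 3% decline by week 48 at 7%: 8.0 / 10.7%.
- No shared session error (other reading): 0.1% at *s* = 5% and 11.1% at 8%.

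**Step 4: selection on worsening, at 7%.**
- Worsening judged only on records before W0: 18.4 / 20.0%, so no inflation.
- Worsening judged with W0, and no true change over the three years: 28.6 / 31.3%, about 15 × 0.30 = 4.5 patients.
- Worsening judged with W0, but an assumed true 10% decline over three years: 18.7% becomes 19.3%, and 20.1% becomes 21.7%.

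**The case against.** **The error is assumed.** Measuring it is one of the study's aims. At 3% the problem disappears, and fewer nerves or continuing decline shrink it. Protocol 5.7.1.1 gives eight as a maximum, counts sensory nerves in it, and allows testing of as few as two limbs. All of this stands, so the size can only be given as a range.

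**Regression to the mean.** A reader might infer that patients chosen for looking worse must rebound, and take 4.5 false responders as the expected count. The documents do not support that. The criterion is a three-year trend, and no section says that W0 counted towards it. The one-day visit makes this possible but does not show it. Step 4 gives no inflation if W0 was not used, and little if the decline was real.

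**MS-SPI.** A reader might infer that the plan contradicts its own precedent. It does not. MS-SPI used a disability score and a timed walk in a randomised design, and Protocol 3.2.3 gives no reason for its best-of-two reference.

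**The earlier EMG may not match.** Nothing requires it to cover the same nerves or all four criteria, or to come from the same laboratory, and it is not among the listed CRF items. This limits the remedy but does not remove it.

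**The study is exploratory.** The responder percentage is descriptive, with no test or decision rule, and per-nerve listings are planned (SAP 10.1.2). That lowers the stakes. It does not tell a reader how many responders to expect by chance.

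**Conclusion.** The point holds in a conditional form. One untreated reading, no control and no confirmation mean that measurement error can produce responders, and the SAP offers no way to judge how many. With eight fully evaluable nerves, no true change and shared session error, the rate runs from under 1% (SD 3%) through about 5–8% (5%) and 18–20% (7%) to 34–35% (10%). Requiring improvement over two untreated readings reduces it to about 0%, 0.4–1%, 3–6% and 11–14%. With four nerves or a 3% decline, the single-baseline rate at 7% falls to roughly 3–11%.

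The documents do not show that any observed responder is spurious, or that regression to the mean occurred. What they do show is that a second untreated record was required for assessing variability and is then left out of the analysis, although variability and robustness are stated aims. That gap is cheap to close.

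**What to change.** In SAP 10.1.1, beside Table 14.4.1.1 and leaving that table unchanged, enter the EMG already required within six months and add:

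- **(a) A chance-rate estimate.** The change from that EMG to W0 for each nerve and criterion, and the share of patients who meet the full success rule between these two untreated readings.
- **(b) A sensitivity responder count.** A nerve-criterion counts as improved only if week 48 is at least 10% better than both the earlier EMG and W0. Where the EMG lacks that nerve or criterion, use W0 alone and flag it.
- **(c) A listing** of which records established worsening for each patient, and whether W0 was among them.

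A new eligibility sentence would come too late: the SAP was signed after all patients had completed (SAP 1). Item (c) is what remains possible.

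**Cost.** Data entry of an existing record, two short tables and a listing; no new patient test. The responder count in (b) will be lower, and matching of nerves and criteria will be incomplete. Where true decline occurred between the EMG and W0, (b) is conservative and (a) understates the chance rate; (a) also understates it if W0 was used for selection. With 15 patients (a) is imprecise: 0 of 15 has an exact 95% upper limit of 21.8%, and 3 of 15 an interval of 4.3% to 48.1%. Report it with its interval.
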